5. STUDY DESIGN

5.1. *Study description*

Observational proof of concept study comparing the ability to redistribute forefoot pressure using a new foot offloading device compared to usual standard care.

The sample will be purposively selected taken from a local population of active diabetic foot ulcer patients. The measurements will be taken from patients wearing usual standard of care, sham shoe (closest to barefoot or baseline pressures) and the PulseFlow DF boot. The measurements from each patient will be collated to compute pti averages for the comparison.

5.2. *Study duration*

Approximately four months or time to complete required maximum sample size of 36 or ending 1st July whichever arrives first.

5.3. *Rationale for study design*

The issue of a novel boot should not influence clinical practice or further research until data is produced to support it.

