6. SELECTION AND WITHDRAWAL OF SUBJECTS

6.1. *Target population*

Patients currently undergoing treatment in the local Diabetic Limb Salvage Service who have diabetic neuropathic related plantar forefoot ulceration.

6.2. *Estimated number of eligible participants*

For this exploratory study formal methods for estimating sample size are inappropriate. The rationale for the size should be based on feasibility and the basis that this study will be used to justify the sample size of future studies. Therefore the rule of thumb modelling over three factors being explored will provide a sample size of 12 in each group (Julious, 2005). Therefore 36 in total are required. From a 2015 audit, theoretically there was a population size of 231 which identified 23% eligible patients for this study. The current population at January 2017 totalled 326 therefore approximately 74 patients should be eligible for this study. From the scoping exercise in December 2016, six patients were approached regarding the study to review possible challenges to taking part. All

Protocol version 1

Evaluating plantar foot pressure in a novel diabetic offloading device

IRAS code 198005

six patients were satisfied with the proposal of taking part considering time required hospital location, travel arrangements and consenting. Therefore it is considered feasible to recruit the required sample of 36 participants (49% of available population following inclusion criteria).

6.3. *Eligibility criteria*

6.3.1. *Inclusion criteria*

- (a) Plantar forefoot diabetic foot ulcer
 - a. over the 1st, 2nd, 3rd, 4th or 5th metatarsal joints
- (b) Neuropathic or Neuro-Ischaemic classification foot ulcer (taken from the TEXAS classification system)
- (c) Orthotic intervention for offloading/usual standard
- (d) English speaking and reading
- (e) Palpable foot pulses and/or Ankle Brachial Pressure Indices of values 0.8 to 1.29.

6.3.2. *Exclusion criteria*

- (a) Being treated for or having an active Charcot Arthropathy
- (b) Ankle Brachial Pressure Indices of <0.8 and >1.29. Using a standardised reproducible instrument called the Huntleigh Dopplex Ability Unit (DA100PB).
- (c) Temporary, accommodating or footwear not designed to offload.
- (d) Clinically active Infection causing lower leg swelling
- (e) Purely ischaemic classification foot ulcer
- (f) Current active osteomyelitis
- (g) Patients with forefoot trans metatarsal or major amputations
- (h) Fractures of the foot

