6.5.3. Randomisation process

Due to the type of study design patients can not be randomised. However the process of measuring usual standard of care, standard shoe and PulsFlow DF can be randomised. This will be performed by using a Latin 3x3 square design below which will be randomly allocated from a computer programme at the appointment time of measuring the foot pressures.

Protocol version 1**Evaluating plantar foot pressure in a novel diabetic offloading device****IRAS code 198005**

Sequence 1	Usual standard care	PulseFlow DF Boot	Standard shoe
Sequence 2	B PulseFlow DF Boot	Standard shoe	Usual standard care
Sequence 3	Standard shoe	Usual standard care	PulseFlow DF Boot

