9.4. Planned analyses

All data will be explored to check for assumptions of normality and homogeneity of variance for each variable, and to assess which statistical tests i.e. parametric or non-parametric test will be more appropriate to explore the data. The assumption of normality will be assessed graphically by histogram, box-plots and confirmed by statistical testing of significance of skewness and kurtosis. The spread, homogeneity and type of data will determine the type of statistical test. The paired t Test is predicted to be the statistical test of choice following statistician advice. This may change due to abnormal distribution of data once collection is complete.

Gait data will be checked for corruption or incomplete results associated with data capture or software error and rectified where possible either at the point of data collection or data analysis.

Exploratory statistical analyses will be performed to identify any potential associations between gait kinematics, clinical data and patient-reported outcomes. We will also explore the data for unexpected findings, including influential outliers, multicollinearity, truncation and missing data.

The primary outcome (section 2.2) will then be compared for systematic differences between the usual standard care and the PulseFlow DF boot using statistical tests based on the assumptions tested previously.

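### No balancing of the three footwear sequences is stated and no period term is planned, so chance imbalance in order may cost the boot versus usual care comparison precision

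*Combined protocol and SAP*

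**What the plan says.** Section 6.5.3 explains that patients are not randomised to a device, because each is measured in all three conditions, but the order of measurement is: "This will be performed by using a Latin 3x3 square design below". The three sequences are usual care–boot–shoe, boot–shoe–usual care and shoe–usual care–boot. The sequence is one "which will be randomly allocated from a computer programme at the appointment time of measuring the foot pressures". The section does not state an allocation ratio, a block size, a list prepared in advance or a target number per sequence.

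Section 6.2 sets the sample size by a pilot-study convention: "rule of thumb modelling over three factors being explored will provide a sample size of 12 in each group", and then "Therefore 36 in total are required". The 12 is per group, not per sequence. Section 5.2 treats this as a "required maximum sample size of 36" and allows recruitment to end earlier on 1 July. Section 6.5.6 allows 36 or more.

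On analysis, section 9.4 says: "The paired t Test is predicted to be the statistical test of choice following statistician advice". The choice may change if the data are not normally distributed. The primary outcome is to be "compared for systematic differences between the usual standard care and the PulseFlow DF boot using statistical tests based on the assumptions tested previously". No period or sequence effect appears in the planned analyses.

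**The concern.** The point of a Latin square is to stop effects of measurement order, such as fatigue or getting used to the laboratory, from mixing with the device effect. In a simple mean of paired differences the period effects cancel exactly only if the three sequences are used equally often. When counts are unequal, the remainder can be removed only by an analysis that models period. As written, the plan secures neither equal counts nor a period term.

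Two uses of the data are affected. The primary objective (section 2.2) is whether pressure time integral with the boot is equivalent to usual care, and that depends on a precise difference. Section 6.2 also says the study will justify the sample size of later studies. An SD of paired differences that still contains period effects would be too large for planning a study that adjusts for period.

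**Working it through.** **Inputs.** N = 36 (section 6.2); three sequences (section 6.5.3); unadjusted paired comparison (section 9.4). Assumed, because the documents are silent: independent draws with probability 1/3 per sequence; linear drift of d per period; paired-difference SD of 1 apart from drift; two-sided 5% test; no carry-over.

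**The plan's own figure.** 12 × 3 = 36, as stated.

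**Sequence counts under simple allocation.**
- P(12/12/12) = 36!/(12!)³/3³⁶ = 0.0226, or 2.3%.
- P(some sequence has 8 or fewer patients) = 31%.
- P(largest minus smallest count is 6 or more) = 1 − 0.506 = 49.4%.

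**What remains in the estimate.** With period effects p1, p2, p3, boot minus usual care carries p2 − p1 in sequence 1, p1 − p3 in sequence 2 and p3 − p2 in sequence 3. These sum to zero only with equal weights. For a linear drift they are +d, −2d and +d, so the mean carries

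d(n1 − 2·n2 + n3)/36 = d(36 − 3·n2)/36 = d(1 − n2/12).

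The expected value of n2 is 12, so the term averages zero. Its SD is d·√(36 × 1/3 × 2/3)/12 = d·√8/12 = 0.236d. The 95th percentile of its absolute value is 5d/12 = 0.417d (n2 = 7 or 17). For example, counts of 9/15/12 leave −0.25d.

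A linear drift cancels whenever n2 = 12, whatever the other counts. That has probability 14.0%, so the 2.3% understates how often this form of drift cancels.

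**Effect on precision.** The contrasts +1, −2, +1 have variance (1 + 4 + 1)/3 = 2. The SD of the estimate is therefore √[(1 + 2d²)/36] under simple allocation and √(1/36) = 0.167 with 12 per sequence.

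| d (in SDs of the paired difference) | SD, simple | SD, 12/12/12 | Increase |
|---|---|---|---|
| 0.1 | 0.168 | 0.167 | 1% |
| 0.25 | 0.177 | 0.167 | 6% |
| 0.5 | 0.204 | 0.167 | 22% |

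Simulation (40,000 studies per setting) agreed to about 0.001.

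**Validity of the test.** In the same simulations the plain paired t test under simple allocation rejected a true null 4.8% to 5.1% of the time for d from 0 to 1.

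**Balance without a period term.** At d = 0.5 with 12/12/12, the true SD of the estimate is 0.167, but the paired t test's mean standard error stays about 0.204. Type I error falls to 0.017. The drift is still inside the SD of the differences, so the confidence interval is too wide.

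**Period term without balance.** Averaging the three sequence means with equal weight removes the period effects whatever the counts. The SD is √[(1/n1 + 1/n2 + 1/n3)/9]. For 9/15/12 this is √[(0.1111 + 0.0667 + 0.0833)/9] = 0.170, close to 0.167.

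**If N is not 36.** Under simple allocation the SD of the shift is d·√(2/N), or 0.32d at N = 20. With blocks of 3, at most one block is incomplete and the leftover term cannot exceed 2d/N: 0.10d at N = 20 and 0.057d at N = 35.

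**The case against.** The strongest reply is that section 6.5.3 never says the draw is unrestricted. A sequence issued by computer at the appointment is compatible with a blocked list prepared beforehand and revealed then. That stands: simple allocation is a reading of a silent text, and 12 per sequence is inferred from 36/3. The supportable statement is that balancing is not specified.

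A reader might also infer that the planned comparison is biased, or that the paired t test is invalid. The documents do not support that. Allocation is random, the leftover term averages zero over allocations, and the test's standard error already reflects it.

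Third, the drift is hypothetical. Section 7.2.1.1 provides a familiarisation tour, 30 minutes to get used to the boot, and measurement only once the patient walks steadily. Section 7.2.1.2 puts data capture for all three devices at 10 to 15 minutes. These steps make a large drift less likely but do not exclude one. At d = 0.1 the loss is about 1%.

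Finally, blocking cannot guarantee equal counts. Recruitment may stop at an N that is not a multiple of 3, and section 6.5.5 destroys the data of patients who withdraw within 24 hours. That also stands. It is a reason to add the period term, not to leave allocation unspecified.

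**Conclusion.** The point holds as a minor, correctable weakness. Neither the stated allocation nor the stated analysis controls period effects in the study as it will be realised. If sequences are drawn simply, a linear drift of d leaves a chance shift with SD 0.24d at N = 36. The SD of the estimate rises by about 1%, 6% or 22% for d of 0.1, 0.25 or 0.5 paired-difference SDs. Without a period term, the variance of the paired differences handed to later studies is inflated by 2d², that is 2%, 12.5% or 50%, relative to a period-adjusted one.

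This rests on assumed simple 1:1:1 draws, linear drift and no carry-over. Because the documents give no drift, SD or margin, practical importance cannot be settled. It should not be read as systematic bias or as a failure of type I error control.

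Equal counts would not balance carry-over in any case: in this single square the boot, when not first, always follows usual care.

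**What to change.** 1. In section 6.5.3, state that the sequences are generated before the first patient in permuted blocks of 3 or 6, with each sequence revealed only at the appointment. This gives 12 per sequence at 36 allocations and near-equal counts if recruitment stops at another number. If a balanced list was already intended, one sentence saying so is enough.
2. In section 9.4, analyse boot minus usual care with a period (sequence) term, for example a Latin-square ANOVA or a mixed model with device and period as fixed effects and patient as a random effect. Report the period-adjusted difference with its confidence interval and the adjusted SD. This lets the interval benefit from the balance and protects against counts that end unequal.

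Both changes are free before recruitment starts: a setting in the allocation programme and one extra term in the model. They add no visits, measurements or burden for participants.

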6.5.4. STUDY BLINDING

Due to the type of study design, patients can not be blinded to the intervention.

6.5.5. Patients who withdraw consent

- As soon as the patient withdraws their consent either verbally or in writing this will be documented within their medical notes within the principal investigators normal working hours.
- If patient withdraws within 24 hours of data collection (of that patient) any data stored for that patient will be destroyed electronically following the organisational IT policy.

6.5.6. Definition for the end of the trial

Numbers completed to the original sample size of 36 or more or by 1st July 2017.

6.6. General information on the products or interventions to be used

PulseFlow DF

The Diabetic Boot Company Ltd, Trading as PulseFlow Technologies, [name].

UK Patent GB 2454089 - Dec 2009

US Patent US 8,388,562 - Mar 2013

FDA Registered Facility - Registration Number: 3012177215, Owner Operator Number: 10051096

PulseFlow DF is indicated for the treatment of active diabetic foot ulcer at the following sites: Plantar aspect of the 1st metatarsophalangeal joint (MTPJ), 2nd - 5th MTPJ, Heel, Plantar and dorsum aspects of the toes and the Dorsum of the foot.

Protocol version 1

Evaluating plantar foot pressure in a novel diabetic offloading device

IRAS code 198005

Proof of concept and pilot studies using healthy and patients with diabetic foot ulcers were used without reporting any adverse reactions. Diabetic foot ulcer patients showed one loss to follow up and one excluded from a small nine patient study to healing. All seven out of the nine patients at study end healed within a six week period.

6.7. ***Use within the trial***

PulseFlow DF Boot

- The PulseFlow DF boot is a trainer design with an integrated ankle foot orthosis. This is made of a metal design to immobilise the ankle and house the battery component around the calf region which will not be in use but with the same weight. Training of application and use of the device will be provided by the company producing the offloading device (Pulseflow Technology).
- The principal investigator will administer and supply the device at the time of data capture. This will be applied and then a recommended period of use will be given before data capture.
- Once the principal investigator and patient are satisfied with the safe use of the device it will be re-applied with the pressure sensing insole inserted.
- There will be no implementation or continuation of the offloading device following completion of data collection. However, information of the device, where it can be purchased from and how much will be offered to the patient as they are currently available to the public and healthcare practitioners.
- A test run will be applied by firstly using it on gait lab engineers and then testing the process on 3 active foot ulcer patients who will not be part of the study. These pre pilot testing phases for the principal investigator will enable training for the principal investigator and identify any anomalies when using the gait lab with study patients for the first time. The selection of the patients will be highly purposive due to the sampling methods and inclusion criteria.

Usual Standard Care

Management of the diabetic foot is guided by NICE with standards on DFU treatments modelled on best evidence (NICE, 2015). The basis of treatments other than TCC is worded as an alternative.

“Offer an alternative offloading device until casting can be provided.”

(NICE, 2015, section 1.5.5)

The alternative is anything available to the service using local protocols or policies and consented to use by the patient. This can be described as below and may be any of the following named devices but is not exhaustive:-

- Bespoke removable Boot (CROW meaning Charcot Restraint Orthotic Walker)
- Removable prefabricated boot e.g. Aircast, DH Walker, Rebound etc.

Protocol version 1

Evaluating plantar foot pressure in a novel diabetic offloading device

IRAS code 198005

- Forefoot offloader
- Rearfoot offloader
- DH Shoe
- Scotch cast boot/shoe/sliper
- Made to measure footwear and total contact/bespoke insoles
- Total contact/bespoke insoles d plantar forefoot ulcer.

7. METHODS OF ASSESSMENT

This will be lab based data collection via electronic software, a modified validated questionnaire and demographic/variable list of specific identifying features of diabetic foot ulcers.

7.1. ***Efficacy assessment variables***

1. Usual care (offloading) device name/description
2. PulseFlow DF
3. Standard shoe

7.2. ***Routine laboratory assessments***

Gait laboratory

Pressure Time Integral

One laboratory will be used within the Leeds Teaching Hospitals NHS Trust. The Gait laboratory is situated within Chapel Allerton Hospital, Leeds. The measurements will be collected on pressure in kPa via the Pedar-xf analyser (novel, no date) automatically collected within self contained password protected computer software package and then held on the secure server of University of Leeds M Drive. This will be stored electronically, password protected (see 8.3.2 for full details) under patient identifiable data (participant study code) for analysis later. The first one collected will be analysed for quality analysis in efficacy and validity issues. Only the research team ill have access to this data.

Questionnaire

A modified validated Measure of Orthopaedic Shoes (MOS) questionnaire will be completed following the pressure measurements. Answers will be recorded on coded patient specific sheet to be collected and uploaded onto a prepared excel data base after the participant has left the appointment.

Protocol version 1

Evaluating plantar foot pressure in a novel diabetic offloading device

IRAS code 198005

The first one collected will be checked for completion. The completed questionnaire documents will be scanned and stored electronically to improve and allow for quality assurance to the transfer of data. This questionnaire will be used for the description analysis of patient acceptability.

7.2.1.1. *Gait analysis details*

Patients will familiarise themselves with the lab with a walking tour taking approximately up to 10minutes with question and answer session on the process of measurement taking and a chance to ask any questions. Then the measurement phase of walk assessment will start approximately 10minutes into the visit. A further 30minutes (total of 40minutes) is allocated to acclimatisation of the novel walking boot before this is used for gathering the measurements.

The combined average of 3 steps or the middle one third of the 30 feet walkway will be used for assessment of PTI. The patient will be blinded from when the time the measurements are taken when walking for the measurement. This will be done by walking with the patient and taking a measurement after the patient has become acclimatised on the measured walkway. Acclimatisation will be quantified by the patient being able to walk and talk without the need of balance assistance i.e. hand on the patient's waist. The middle third of the walk will be used to acquire the measurements of PTI (approximately 3 steps of the foot)

7.2.1.2. *Duration of gait analysis*

Approximately 60 minutes will be given per patient visit to allow for technical and practical issues within the gait measuring room. The process for taking the electronic data measurements is estimated to take between 10 and 15minutes for all three devices however the overall practical process will take longer. The participant will then be allowed to complete the short questionnaire needed for the secondary analysis. This will take no longer than an additional 10minutes.

General Safety

Those experiencing hypoglycaemia from their diabetes at time of measurements will need to be addressed for patient safety reasons. Hypoglycaemia is measured or determined by the patient or the symptoms related to hypoglycaemia i.e. shaking, unbalanced walking, speaking incoherently, slow/slurred speech, sweating, feeling hot, disorientated and measured low blood sugars via the patient's blood sugar machine. When any participant has a hypoglycaemic event or becomes unwell the proceedings will be stopped. Hypoglycaemic events are not considered to

Protocol version 1**Evaluating plantar foot pressure in a novel diabetic offloading device****IRAS code 198005**

be caused by the intervention. The researcher will then seek appropriate medical care. The use of the nursing out patient hospital setting where the gait lab is situated will be used as support to any first aid issues. More serious events will be referred as appropriate to the nearest emergency care services. Rearranging the appointment will be offered following recovery.

7.2.1.3. *Data capture*

Data will be via the CE marked Novel Pedar Inshoe pressure analysis system. This system has been shown to have a higher accuracy than a similar competitor (Hsiao et al., 2002). It has also been piloted in a small study looking at sensitivity and valuable in post ulceration footwear analysis (Giacomozzi and Uccioli, 2013).

7.2.1.4. *Data analysis*

IBM SPSS Statistics 22 software will be used to analyse data. See 9.4.

8. STUDY MANAGEMENT AND ADMINISTRATION**8.1. *Good clinical practice (GCP)***

This clinical trial will be run in accordance with the Principles of ICH GCP and the Research Governance Framework 2005.

8.2. *Adherence to protocol*

The Investigator should not deviate from the protocol. In medical emergencies, the Investigator may use his/her medical judgment and may remove a study participant from immediate hazard before notifying the Sponsor and the REC in writing regarding the type of emergency and the course of action taken.

8.3. *Data handling***8.3.1. *CRF completion***

The research team is responsible for prompt reporting of accurate, complete, and legible data in the CRFs and in all required reports. Any change or correction to the CRF should be dated, initialled, and explained (if necessary) and should not obscure the original entry. Use of correction fluid is not permitted. The Investigator is the sole authorizer to enter data into the CRF. Detailed instructions will be provided in the CRF Instructions.

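### Minor: Section 7.2.1.1 does not place the boot's 30-minute acclimatisation within the randomised device order; state that it precedes all recordings, balance the sequences and add a period term

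*Combined protocol and SAP*

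**What the plan says.** All references are to the combined protocol and SAP.

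- **Device order (6.5.3).** Three measurements are taken per patient, in an order set by a Latin square: "This will be performed by using a Latin 3x3 square design below which will be randomly allocated from a computer programme". The printed sequences are usual care, boot, shoe (Sequence 1); boot, shoe, usual care (Sequence 2); shoe, usual care, boot (Sequence 3). Equal numbers per sequence are not stated.
- **Visit timing (7.2.1.1).** After a tour of up to about 10 minutes, "Then the measurement phase of walk assessment will start approximately 10minutes into the visit". The next sentence reserves time for the boot only: "A further 30minutes (total of 40minutes) is allocated to acclimatisation of the novel walking boot before this is used for gathering the measurements".
- **Acclimatisation check (7.2.1.1).** A functional criterion with no time attached, and not limited to the boot: "Acclimatisation will be quantified by the patient being able to walk and talk without the need of balance assistance".
- **Duration (7.2.1.2).** "Approximately 60 minutes will be given per patient visit", and "The process for taking the electronic data measurements is estimated to take between 10 and 15minutes for all three devices". The same section adds that the whole practical process takes longer, and allows up to 10 further minutes for the questionnaire.
- **Boot handling (6.7).** The investigator supplies the boot when data are captured. A spell of use comes before capture, and then "it will be re-applied with the pressure sensing insole inserted". The section does not say whether this means capture for the boot or for all devices.
- **Analysis (9.4).** A paired t test is expected for boot against usual care. No period term is mentioned.

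**The concern.** Extra time in an unfamiliar boot is sensible and is not the issue. The issue is where that time sits. In two of the three sequences the boot follows usual care. If the 30 minutes are inserted just before the boot recording, those patients have usual care recorded early in the visit and the boot more than half an hour later. The Latin square would then balance position in the order but not time elapsed in the visit.

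If PTI changed during the visit, for example through fatigue or growing ease with the walkway, part of that change would appear in the boot minus usual-care difference, which is the primary comparison. More patients would not average it out. The offset also differs between sequences, so drift would widen the SD of the paired differences, and 6.2 intends this study to justify the size of later ones.

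Separately, 6.5.3 and 9.4 randomise device order without securing balance between sequences or using period in the analysis.

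**Working it through.** **The plan's own figure.** 10 minutes (tour) + 30 minutes (boot) = 40 minutes, as printed in 7.2.1.1.

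**Inputs.** Measurement starts at about minute 10 (7.2.1.1). The boot block is 30 minutes (7.2.1.1). Three recordings take 10 to 15 minutes (7.2.1.2), so r = 10/3 to 15/3 = 3.3 to 5 minutes each; the equal split is an assumption. Let a be the untimed walk-in for each of the other two devices; the documents give no value, so 0 to 5 minutes is assumed. Offset = boot recording start minus usual-care recording start.

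**Placement A: block before all recordings.** Only position in the order separates the devices.

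| Sequence | Offset | r = 3.3 | r = 5 |
|---|---|---|---|
| 1 | r | +3.3 | +5 |
| 2 | -2r | -6.7 | -10 |
| 3 | r | +3.3 | +5 |

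Mean (r - 2r + r)/3 = 0 with equal sequences; SD across patients r√2 = 4.7 to 7.1 minutes. The mean stays 0 if each device, including the re-applied boot, gets the same short walk-in.

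**Placement B: block just before the boot recording, a = 0.**

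| Sequence | Usual care starts | Boot starts | Offset |
|---|---|---|---|
| 1 | 10 | 40 + r | 30 + r |
| 2 | 40 + 2r | 40 | -2r |
| 3 | 10 + r | 40 + 2r | 30 + r |

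Mean (30 + r - 2r + 30 + r)/3 = 60/3 = 20 minutes, whatever r is. SD (10 + r)√2 = 18.9 to 21.2 minutes.

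**Placement B with walk-in.** The Sequence 2 offset becomes -(2r + 2a) and the others do not change, so the mean is 20 - 2a/3: 18.3 at a = 2.5 and 16.7 at a = 5. With r = 3.3 and a = 5 the visit is full before the questionnaire: 10 + 30 + 10 + 2 × 5 = 60 minutes.

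**Does the square or a period term remove the offset in B?** Mean position is the same for both devices: boot (2 + 1 + 3)/3 = 2 and usual care (1 + 3 + 2)/3 = 2. With equal sequences, device and period are orthogonal, so the period-adjusted offset equals the difference in mean start times: (40 + r) - (20 + r) = 20. A least-squares fit of start time on device, period and patient also gives 20.0 for 14/7/15 and 10/17/9 patients in Sequences 1 to 3 (16.7 when a = 5). The period term does not remove it.

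**Sequence balance.** If allocation is simple random (an assumption, since 6.5.3 does not say), exactly 12/12/12 has probability 36!/(12!³ × 3³⁶) = 2.3%. Sequence 2 holds 7 to 17 of 36 patients with probability 95% (binomial, 1/3). Under A the mean offset with n₂ patients in Sequence 2 is r(1 - n₂/12): +1.4 to +2.1 minutes at n₂ = 7 and -1.4 to -2.1 at n₂ = 17. With a period term it is 0 in both cases.

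**The case against.** The strongest reply is that the plan probably already intends the harmless placement. Read as visit time, the two printed figures (30 minutes of boot acclimatisation, finished at minute 40) are both met in every sequence only if the block comes first. Run just before the boot, the block would end at 40 + r or 40 + 2r, that is 43 to 50 minutes, in Sequences 1 and 3. Section 6.7, which puts the spell of use ahead of data capture, points the same way. This stands, and it is why the point is minor. It does not close the matter: the wording in 7.2.1.1 ties the block to the boot's own use, measurement is said to start at about minute 10, and 6.7 supplies the boot when data are captured. Placement B therefore remains open.

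A reader might infer more than the documents support:

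- **That the boot comparison is biased.** No document gives a drift in PTI, in size or direction. Minutes cannot be converted into PTI, and with no drift there is no effect.
- **That the boot could be held at minute 40 with measurement starting at minute 10, giving an offset of 20 - r = 15.0 to 16.7 minutes.** That cuts boot acclimatisation to 30 - r or 30 - 2r, i.e. 20 to 27 minutes, in Sequences 1 and 3, against the 30 stated.
- **That placement may vary from visit to visit.** One investigator collects all data in one laboratory after test runs (9.1, 7.2, 6.7), and nothing suggests varying practice.

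It is also fair to say that balanced allocation alone is worth only about 2 minutes of offset under block-first, and that a device-plus-period model does not deal with carry-over. The printed square is cyclic: a device that is not first always follows the same predecessor. Both points stand. They limit the gain but do not argue against steps that cost almost nothing.

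**Conclusion.** This is a minor, inexpensive improvement. The place of the boot-only block in the randomised order is not stated. The best-fitting reading gives a mean boot minus usual-care recording-time offset of 0 with equal sequences. The other permitted reading gives about 20 minutes, or 16.7 to 20 with up to 5 minutes of walk-in for the other devices, and a period term does not remove it. The figures rest on an equal split of recording time, equal use of the three sequences, and the assumed walk-in. The effect on PTI is unknown and depends entirely on within-visit drift. Apart from placement, the design would make better use of the order it randomises if sequence numbers were balanced and period entered the analysis.

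**What to change.** 1. **Section 7.2.1.1.** State that boot familiarisation is completed before any recording in every sequence, and that the existing walk-and-talk check is then applied to each device. Add no timed walk in the standard shoe, which 5.1 describes as a "sham shoe (closest to barefoot or baseline pressures"). Include a short seated rest with the boot off if the visit allows. Without it, the time before the questionnaire is 10 + 30 + 10 to 15 = 50 to 55 minutes, leaving 5 to 10 of the planned 60. A full 10-minute rest gives 60 to 65. The downside is that usual care follows boot wear in 3 of 3 sequences, against 1 of 3 if the block ran just before the boot. The rest reduces carry-over but cannot exclude it. If block-first is already intended, this downside is already present.
2. **Section 6.5.3.** Allocate the three sequences in balanced blocks, for example of 6. This gives 12/12/12 at 36 patients and keeps the counts within 2 of each other if recruitment stops on 1 July (5.2). The cost is one prepared list.
3. **Section 9.4.** Keep the paired t test and accompany it with a model for PTI with device and period as fixed effects and patient as a random effect. This covers position effects and small imbalances. It does not address carry-over and would not rescue placement B. The cost is one supporting analysis.

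No extra patients are needed.
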